The Cue and Stress Response Task will be performed at the 5- week time-point using methodology developed in [name]'s lab, similar to those in used in past studies with alcohol dependent patients [112, 113]. [name] will provide consultation on the implementation of these methods. Briefly, imagery scripts will be developed at baseline and again following 4 weeks of treatment. Stress imagery scripts will be based on a recent highly stressful situation the participant has experienced unrelated to alcohol use. Alcohol cue scripts will be derived from a recent event that included alcohol-related stimuli and led to alcohol use. Neutral or relaxing scripts will also be developed. All scripts will be developed by obtaining specific details of stimulus and response, including contextual details, cognitive and verbal content, affective experience, and bodily sensations. These details form the basis of a 5-minute imagery script, which will be developed for each of the three conditions. Imagery sessions will be structured with a 5-minute pre-imagery period, a 5-minute imagery period, and a 5-minute recovery period. Pulse, skin conductance, heart rate variability, and blood pressure will be monitored during each imagery session with an ADInstruments PowerLab 4/30 Galvanic Skin Response device and a Contec Patient Monitor. In Human laboratory studies with CBD, skin conductance and amygdala activation were reduced by CBD in a closely correlated manner [59], suggesting threat-related sympathetic arousal may serve as a proxy for amygdala activation [114]. Participants will complete Likert scale ratings of vividness, craving, anxiety, and the 30-item Differential Emotion Scale [112, 113] following each of the three periods. After each condition, a progressive relaxation procedure will be implemented to facilitate return to baseline of vital signs, craving and anxiety, an approximate period of 10 minutes, as shown in previous research from the [name] lab [112, 113]. The entire imagery protocol will take 120 minutes. The order of the sessions will be randomized and counterbalanced among participants. This task will be completed at 5 weeks, i.e. after 1 week of treatment at 1200mg daily. At this point, we expect steady-state circulating CBD levels to have been reached. It is important to assess stress- and cue- response at the high dose because it is possible that anxiolytic effects decrease at high doses of CBD, while effects on alcohol consumption are expected to increase with dose.

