21.3 Description of Statistical Methods

21.3.1 General Approach

The distributional characteristics of the measures used to investigate the aims of the study will be assessed and data transformations will be explored if necessary. For all hypotheses, linear mixed effects models will be constructed including treatment group as a fixed between-subjects factor, time (T0-T9) as a fixed within-subjects factor, and subject as a random effect. Treatment groups will also be compared on baseline measures of alcohol consumption (% drinking days and % heavy drinking days), alcohol craving (PACS), anxiety (BAI), mood (BDI-II), and self-efficacy (AASE), and baseline scores on these measures will be utilized as covariates for hypothesis evaluation.

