21.3.3 Analysis of the Secondary Endpoint(s)

For Hypothesis 2a, between- and within- group differences on measures of craving, anxiety, depression, and self-efficacy (T1, T3, T4, T6, T7, T8) will be evaluated. For Hypothesis 2b, linear mixed effects models will be constructed as described by [name] et al. [123] with treatment group (CBD vs. placebo) included as a fixed

CONFIDENTIAL

This material is the property of the NYU School of Medicine and Langone Health
Do not disclose or use except as authorized in writing by the study sponsor

between-subjects factor, time (nested factor including pre-imagery, imagery, and recovery periods at both T3 and T6) and script type (stress, alcohol cue, neutral) as fixed within-subjects factors, with subject as a random effect. Between- and within- group comparisons and interactions for measures of craving, anxiety, and physiological stress response will be assessed.

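### The Hypothesis 2b model names only a subject random effect, although three ratings share each script session: period-averaged script contrasts get standard errors that are too small, and the induced change generally gets ones that are too large.

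*Combined protocol and SAP*

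**What the plan says.** Section 21.3.3 gives the Hypothesis 2b model, with treatment group between subjects. The script factor and the random part read "script type (stress, alcohol cue, neutral) as fixed within-subjects factors, with subject as a random effect". The repeated ratings within a task enter through another fixed factor, worded as "time (nested factor including pre-imagery, imagery, and recovery periods at both T3 and T6". The description opens with "For Hypothesis 2b, linear mixed effects models will be constructed as described by" a cited lofexidine study. It promises between- and within-group comparisons and interactions, but does not say which one is the 2b test. Section 21.3.1 sets the same rule for all hypotheses: "time (T0-T9) as a fixed within-subjects factor, and subject as a random effect".

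Section 5.1.2, repeated in 8.1, describes the data. On the structure of a session it says "Imagery sessions will be structured with a 5-minute pre-imagery period, a 5-minute imagery period, and a 5-minute recovery period". On what is rated, and when, it says "Participants will complete Likert scale ratings of vividness, craving, anxiety, and the 30-item Differential Emotion Scale [112, 113] following each of the three periods". On sequence it says "The order of the sessions will be randomized and counterbalanced among participants". Each person therefore gives three ratings in each of three separately ordered sessions.

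On timing, 5.1.2 says "This task will be completed at 5 weeks, i.e. after 1 week of treatment at 1200mg daily", and the visit lists in 8.3.3 show the task at T6 and not at T3. Section 21.3.3 has it at both T3 and T6.

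**The concern.** A single subject intercept treats all of a person's ratings as equally correlated. Ratings within one session share a script, a place in the order and a momentary state, so they should be more alike than ratings from different sessions. The word nested in 21.3.3 describes a fixed factor and adds no random term.

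The model then tests every within-person contrast against one pooled residual, whether the contrast lies between sessions or within one. Hypothesis 2b (21.2) concerns stress- and cue-induced response, which is a within-session change. With about 40 participants there is little power to lose. Because 21.3.3 leaves the test unnamed and 21.3.8 applies no multiplicity correction, a script-level group difference with an understated error could also be reported as support for 2b.

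**Working it through.** **The plan's own figure.** Section 21.4 says 2b is powered at 0.95 for d = 0.3 with 40 participants and alpha 0.05. A two-sample t test with 20 per arm detects d = 1.17 (two-sided). A repeated-measures group-by-time test comes near 0.3 only with unstated inputs; for example, 18 ratings with correlation 0.5 give d = 0.287. The figure can be neither confirmed nor refuted, and nothing below depends on it.

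**Inputs.** From the documents: 20 per arm (40 randomised 1:1, section 5.1), 3 sessions × 3 ratings (5.1.2), alpha 0.05 (21.4). Assumed: total variance 1, between-person share 0.5, session variance τ² = 0.05 to 0.30, residual σ² = 0.5 − τ², task at T6 only.

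**Pooled error.** Nine ratings leave 8 within-person df: 2 between sessions, with expected mean square σ² + 3τ², and 6 within sessions, with σ². The subject-only model pools them:

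[2(σ² + 3τ²) + 6σ²]/8 = σ² + 0.75τ², on 40 × 8 − 16 = 304 df (critical t 1.968).

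If the task is done at T3 and T6, it becomes [5(σ² + 3τ²) + 12σ²]/17 = σ² + 0.88τ².

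**Correct error, on the same scale.**
- Script contrast averaged over periods: σ² + 3τ²
- Script contrast at one period: σ² + τ²
- Change within a session, or that change minus the neutral change: σ²

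With k = √(pooled/correct), the nominal 5% test rejects a true null with probability P(|t₃₀₄| > 1.968k). At τ² = 0.20, pooled = 0.30 + 0.15 = 0.45. For the script average, k = √(0.45/0.90) = 0.707, giving 16.5%. For the change, k = √(0.45/0.30) = 1.225, giving 1.7%.

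| τ² | Pooled | Script average: k, rejects | Script, one period: k, rejects | Change: k, rejects | Power of change test |
|---|---|---|---|---|---|
| 0.05 | 0.4875 | 0.901, 7.7% | 0.987, 5.3% | 1.041, 4.1% | 80% |
| 0.10 | 0.475 | 0.824, 10.6% | 0.975, 5.6% | 1.090, 3.3% | 77% |
| 0.20 | 0.45 | 0.707, 16.5% | 0.949, 6.3% | 1.225, 1.7% | 68% |
| 0.30 | 0.425 | 0.622, 22.2% | 0.922, 7.1% | 1.458, 0.4% | 50% |

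The last column is Φ(2.88 − 1.968k); 2.88 is the noncentrality at which a per-person contrast test (38 df) has 80% power. Simulation agrees: about 8–22% for the script average and 4.5–0.6% for the change. In REML fits with session share 0.3 of within-person variance, adding the session term moved the average standard error of group-by-script from 0.247 to 0.322, and of group-by-change from 0.427 to 0.373. The T3-and-T6 layout gives the same directions: over within-person shares 0.1 to 0.7, k runs from 0.91 to 0.62 for the script average and from 1.05 to 1.75 for the change.

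**If people differ in general reactivity to imagery.** Add a subject-by-period variance ω². The pooled error becomes σ² + 0.75(τ² + ω²). The correct errors become:
- One script's change: σ² + ω². Its standard error is still too large unless ω² > 3τ².
- Stress or cue change minus neutral change: σ². Its standard error is still too large.
- Change averaged over stress and cue: σ² + 2ω². Its standard error is too small once ω² > 0.6τ².

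For that average, with τ² = 0.10:
- ω² = 0.10 (σ² = 0.30): pooled 0.45 against 0.50, rejecting 6.3% (simulated 6.0%).
- ω² = 0.20 (σ² = 0.20): pooled 0.425 against 0.60, rejecting 9.9% (simulated 10.0%).

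A session intercept alone leaves a within-session residual of [2(σ² + 3ω²) + 4σ²]/6 = σ² + ω² = 0.40 in both cases. It rejects 7.9% and 10.9% (simulated 7.8% and 11.1%).

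**Section 21.3.1.** Visits at weeks 0, 1, 4, 5, 8 and 9 were simulated with an assumed weekly correlation of 0.8 to 0.95. An unadjusted T7-minus-T1 group contrast rejects 11–13% if correlation is pure AR(1). With the baseline adjustment that 21.3.1 plans, the T7 test rejects 6.7–9.8%. Adding a stable person share of 0.3 and measurement error of 0.2 brings it to 6.0–7.1%.

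**The case against.** The strongest reply is that the covariance is unstated rather than wrong. Sections 21.3.1 and 21.3.3 name subject as a random effect without saying it is the only one. Section 21.3.3 defers to a cited study, and 21.1 promises a formal SAP before lock. Either could add structure, and neither is available here. Still, subject is the only random term named, and an analyst following the text would fit the model examined above.

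Four limits stand:
- The size rests on assumed variance components. At a session share of 0.05 the effect on the induced change is minor.
- A reader might infer that Hypothesis 2b itself faces 8–22% false positives. The documents do not support that: those rates belong to a script contrast averaged over all three periods, whereas 21.2 states an induced response, for which the test is generally conservative.
- A reader might infer that a session intercept alone is the cure. It is not when reactivity varies between people: the change averaged over stress and cue then does worse than under the planned model.
- A reader might carry 11–13% over to the visit contrasts in 21.3.1. That figure needs pure AR(1) and no baseline adjustment, and 21.3.1 plans the adjustment.

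**Conclusion.** The point holds, conditional on session variance above zero. As written, the 2b model gives standard errors that are too small for group-by-script contrasts averaged over periods, and generally too large for the within-session change that 2b concerns. Over the assumed session shares of 0.05–0.30, the change test keeps between almost all of an 80% power and about 50%. Single-period script contrasts reject about 5–7%, and the overall CBD–placebo effect is unaffected. The direction for the change is not universal: averaged over scripts, it can have too small an error if reactivity to imagery varies between people. In 21.3.1 the same simplification matters less, at about 6–10% for the baseline-adjusted T7 test under the correlations assumed.

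**What to change.** In 21.3.3, define the 2b test as the CBD–placebo difference in imagery-minus-pre-imagery change for the stress and alcohol cue scripts, either alone or minus the neutral change. Test it in one of two ways:
- on one contrast per person, compared between arms; or
- in a mixed model with subject, subject-by-script (session) and subject-by-period random effects, plus subject-by-visit if the task is done at both T3 and T6.

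Reconcile 21.3.3 (T3 and T6) with 5.1.2, 8.1 and the visit lists in 8.3.3 (week 5).

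In 21.3.1, let correlation depend on the gap between visits, for example subject plus continuous-time AR(1), with Kenward–Roger degrees of freedom. Use an unstructured covariance only where the numbers support it: six visits need 6 × 7/2 = 21 parameters, and the seven post-dose visits of Hypothesis 1a need 28 from about 20 CBD-treated people.

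The cost is wording in a SAP that 21.1 says is still to be written, a few more variance parameters and some added analysis work. No data collection changes unless reconciling the visits requires it.

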21.3.4 Safety Analyses

Means and standard deviations of acute circulating CBD and THC levels within CBD-treated participants 45 minutes after initial administration (T1, T4), and 45 minutes after administration of the morning dose of medication following 1 day (T2, T5), 1 week (T3, T6), and 4 weeks (T4, T7) of treatment with each dose of CBD will be assessed to determine whether target circulating levels of CBD have been achieved, and whether metabolic transformation of CBD to THC has occurred.

Means and standard deviations of change in 12 hour circulating CBD levels from 1 week to 4 weeks of treatment (T3 to T4, and T6 to T7) within CBD-treated participants will be presented to determine whether extended treatment with CBD results in accumulation of CBD.

The number of participants within each treatment group that were able to pass a battery of psychomotor field sobriety tasks (walk-and-turn task, one-leg stand, Romberg's test, finger-finger test, and counting backwards [97]) within 2 hours of the initial administration of each dose of CBD vs. placebo (T1 and T4) will be analyzed as summary statistics during treatment.

AEs and SAEs, when present, will be collected on an AE Case Report Form at study visits. The form will include an assessment of clinical significance and study relatedness. Serious Adverse Events (SAEs) will be documented on an additional SAE form. These CRFs will be based on those used in recent NIDA Clinical Trials Network trials. To further assess abuse potential, visual analog scales will be used to assess abuse potential. Scales will include desire to use the study medication again, desire to use the study medication again for pleasurable intoxication ("to get high"), and craving for the study medication.

The study may be stopped if there are untoward and concerning levels of Adverse Event (AE) or Serious Adverse Event (SAE) outcomes attributable to CBD or study participation. If the DSMB finds it is likely that CBD is contributing to negative outcomes, they will consider solutions including protocol changes or potentially stopping the study.

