Objectives	To assess circulating cannabinoid (including CBD and THC) levels and safety of CBD administered to patients with AUD, to contrast the effects of CBD to those of placebo on several physiological and psychological domains relevant to AUD, and to assess the impact of CBD on drinking behavior
Methodology	Double-blind, placebo-controlled
Endpoint	Circulating concentrations of CBD and THC, AEs, and scores on psychomotor and cognitive tasks and alcohol consumption.
Study Duration	2 years
Participant Duration	12 weeks
Duration of IP administration	8 weeks
Population	n=40 18-65 year-old males and females with moderate to severe alcohol use disorder in the New York area
Study Sites	New York University School of Medicine
Number of participants	60 participants expected to be enrolled
Description of Study Agent/Procedure	Cannabidiol PO 600-1200mg/day
Reference Therapy	Placebo with medication management
Key Procedures	Blood draws
Statistical Analysis	Circulating levels of CBD, Anandamide, Delta-9 THC, 11-Hydroxy Delta-9 THC and Delta-9 Carboxy THC will be assessed in CBD-treated participants 45 minutes after the initial administration (T1, T4), 1 day (T2, T5), 1 week (T3, T6), and 4 weeks (T4, T7) of treatment with each dose of CBD. Anandamide levels will also be assessed at these timepoints in placebo treated participants. Additionally, circulating levels of CBD and anandamide will be assessed in CBD-treated participants 12 hours after ingestion of the preceding evening dose following 1 week (T3, T6) and 4 weeks (T4, T7) of administration of each dose of CBD. Circulating levels of each analyte (mean and standard deviation) will be reported at each timepoint, and effects of dose and time-point will be evaluated. Between-group differences on psychomotor tasks (T1-T8), cognitive measures (T3, T6) and number of adverse events (T1-T9) will be assessed.

CONFIDENTIAL

This material is the property of the NYU School of Medicine and Langone Health
Do not disclose or use except as authorized in writing by the study sponsor

1 Schematic of Study Design

CONFIDENTIAL

This material is the property of the NYU School of Medicine and Langone Health
 Do not disclose or use except as authorized in writing by the study sponsor

2 Key Roles

[name] – Principal Investigator

New York University School of Medicine
Department of Psychiatry
[name]
[contact]
[contact]

[name] Sub-Investigator

New York University School of Medicine

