3.2.3 Dose Rationale (if applicable)

CBD has been given up to 600 mg daily orally for cannabis dependence [80], and the one existing human study of CBD's impact on the acute effects of alcohol used a dose of 200 mg [88]. CBD was given to patients with schizophrenia up to 1280 mg/day [89], and Phase 3 trials of CBD for seizure disorders used doses of 20 mg/kg/day oral CBD solution (1400 mg/day for a 70 kg person) [9, 11].

Consistent and clinically significant effects on fear and anxiety in the absence of intoxicating, psychotomimetic, and psychotropic effects have been observed with oral dosing in the range of 300-600 mg/day [90]. However, preliminary work performed by [name] and others [76] indicates that higher doses (>30mg/kg/day transdermal/subcutaneous) yielding serum CBD concentrations in the range of 300-400ng/ml are required to reduce alcohol-reinforced reward-seeking behaviors in rodents.

Oral dosing of CBD is complicated by limited oral absorption, which is similar to THC at approximately 6% [91], and by the possibility that high doses of CBD could convert to THC when delivered orally [92, 93]. However, oral delivery of CBD in a sesame-oil formulation at a dose of 12mg/kg (roughly equivalent to 1000mg/day adjusted for average human body weight) was shown to yield serum concentrations within the targeted range in rats [94]. We therefore will administer CBD vs. Placebo orally in a lipid-based formulation at 600mg/day for an initial period of 4 weeks, followed by 1200mg/day for an additional 4 weeks, to reach our target circulating levels of 300-400ng/ml in a human AUD sample. Two studies in humans have shown no progressive accumulation of CBD levels with repeated daily dosing, including following 6 weeks of oral administration of 700mg/day CBD [95, 96], and preliminary data with transdermal CBD up to 30mg/kg/day in rodents shows no serum accumulation over 7 days of treatment ([name], unpublished data). Therefore, under the proposed dosing regimen we expect to achieve steady-state circulating levels of CBD within a week.

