Plasma CBD, Delta-9 THC, 11-Hydroxy Delta-9 THC, Delta-9 Carboxy THC, and Anandamide levels will be assessed prior to the first dose (T1), 45 min after ingesting the first dose (T1), and 45 min after ingesting the morning dose after 1 day (T2, T5), 1 week (T3, T6), and 4 weeks (T4, T7) of treatment with each dose of CBD (600mg/day, 1200mg/day). Anandamide levels will also be assessed at these timepoints in placebo treated participants. We will also assess pre-CBD dosing plasma levels of CBD and Anandamide prior to ingesting the morning dose after 1 week (T3, T6) and 4 weeks (T4, T7) of treatment with each dose of CBD. Anandamide levels will also be assessed at these timepoints in placebo-treated participants.

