5.1.1 Primary Study Endpoints

Circulating cannabinoid levels

Circulating levels of CBD, Anandamide, Delta-9 THC, 11-Hydroxy Delta-9 THC and Delta-9 Carboxy THC will be assessed in CBD-treated participants 45 minutes after the initial administration (T1, T4), 1 day (T2, T5), 1 week (T3, T6), and 4 weeks (T4, T7) of treatment with each dose of CBD. Anandamide levels will also be assessed at these timepoints in placebo treated participants. Additionally, circulating levels of CBD and anandamide will be assessed in CBD-treated participants 12 hours after ingestion of the preceding evening dose following 1 week (T3, T6) and 4 weeks (T4, T7) of administration of each dose of CBD. Plasma CBD levels will be determined via High Performance Liquid Chromatography/Tandem Mass Spectrometry (LC-MS/MS) by collaborators at the Nathan Kline Institute.

Safety

Safety will be assessed by collection of adverse events at all visits after treatment is initiated. LFTs will be obtained at screening, as well as weeks 4, 8, and 9 to assess liver function during and after treatment with study medication. Risk of suicidality will be assessed using the Columbia-Suicide Severity Rating Scale (C-SSRS) [111] by a licensed Clinical Psychologist, NP or MD as part of each study visit (except for the 1-day/T2 and 4 weeks+1-day/T5 visits).

Psychomotor and subjective effects of CBD:

Basic motoric and cognitive function will be evaluated throughout treatment with several established field sobriety tests, including a walk-and-turn task, one-leg stand, Romberg's test, finger-finger test, and counting backwards [97]. The Addiction Research Center Inventory (ARCI), 49-item version [98], will be used as a measure of the intoxicating effects and abuse potential of CBD. Breath Alcohol Concentration (BAC) will also be measured to ensure participants are not under the influence of alcohol during administration of these tasks. Between-group differences on psychomotor tasks (T1-T8), cognitive measures (T3, T6) and number of adverse events (T1-T9) will be assessed.

Cognitive Function:

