8.3.3 Intermediate Visits

8.3.3.1 Visit 2

1 day (T2)

CONFIDENTIAL

This material is the property of the NYU School of Medicine and Langone Health
Do not disclose or use except as authorized in writing by the study sponsor

- Collect blood for CBD, Delta-9 THC, 11-Hydroxy Delta-9 THC, Delta-9 Carboxy THC and Anandamide levels (45 minutes post-CBD levels)
- Record adverse events as reported by participant or observed by the coordinator
- Record vital signs, results of evaluations of safety, and psychomotor effects

8.3.3.2 Visit 3

1 week (T3)

- Collect urine for urine drug analysis and urine pregnancy test
- Collect blood for CBD, Delta-9 THC, 11-Hydroxy Delta-9 THC, Delta-9 Carboxy THC and Anandamide levels (pre-CBD and 45 minutes post-CBD levels)
- Record adverse events as reported by participant or observed by investigator
- Record vital signs, results of evaluations of safety, psychomotor/subjective effects, cognitive function, AUD-related domains and drinking
- Provide additional medication to the participant according to the study's MOP requirements
- Record participant's adherence to treatment program

8.3.3.3 Visit 4

4 weeks (T4)

- Collect urine for urine drug analysis and urine pregnancy test
- Collect blood for CBD, Delta-9 THC, 11-Hydroxy Delta-9 THC, Delta-9 Carboxy THC and Anandamide levels (pre-CBD and 45 minutes post-CBD levels), LFTs
- Collect blood for CDT levels
- Record adverse events as reported by participant or observed by investigator
- Record vital signs, results of evaluations of safety, psychomotor/subjective effects, AUD-related domains, and drinking
- Provide additional medication to the participant according to the study's MOP requirements
- Record participant's adherence to treatment program

8.3.3.4 Visit 5

4 weeks + 1 day (T5)

- Collect blood for CBD, Delta-9 THC, 11-Hydroxy Delta-9 THC, Delta-9 Carboxy THC and Anandamide levels (45 minutes post-CBD levels)
- Record adverse events as reported by participant or observed by coordinator
- Record vital signs, results of evaluations of safety, psychomotor/subjective effects

8.3.3.5 Visit 6

5 weeks (T6)

- Collect urine for urine drug analysis and urine pregnancy test
- Collect blood for CBD, Delta-9 THC, 11-Hydroxy Delta-9 THC, Delta-9 Carboxy THC and Anandamide levels (pre-CBD and 45 minutes post-CBD levels)
- Record adverse events as reported by participant or observed by investigator.

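### Section 21.3.4 judges CBD-to-THC conversion from group means and SDs of THC at 45 minutes, with no participant count, T1 baseline or metabolites, so conversion in a minority can be missed or left unquantified

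*Combined protocol and SAP*

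**What the plan says.** Section 3.2.3 says oral dosing is complicated "by the possibility that high doses of CBD could convert to THC when delivered orally". Section 21.3.4 takes this up with "Means and standard deviations of acute circulating CBD and THC levels within CBD-treated participants 45 minutes after initial administration" and at the later 45-minute samples through T7, one purpose being to determine "and whether metabolic transformation of CBD to THC has occurred". It states no threshold, participant count, baseline or rule for values below the assay limit. Section 21.3.9 excludes individual response data other than AEs and SAEs.

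Both metabolites are listed with THC and CBD among the primary endpoints in 5.1.1. The Statistical Analysis row of the Protocol Summary names the same panel and says: "Circulating levels of each analyte (mean and standard deviation) will be reported at each timepoint, and effects of dose and time-point will be evaluated".

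The documents differ on the pre-dose samples taken during treatment. Section 5.1.1 says "circulating levels of CBD and anandamide will be assessed in CBD-treated participants 12 hours after ingestion of the preceding evening dose". Section 3.2.3 agrees: "We will also assess pre-CBD dosing plasma levels of CBD and Anandamide prior to ingesting the morning dose". The visit list for T3 in 8.3.3 instead says: "Collect blood for CBD, Delta-9 THC, 11-Hydroxy Delta-9 THC, Delta-9 Carboxy THC and Anandamide levels (pre-CBD and 45 minutes post-CBD levels". T4, T6 and T7 have the same analytes and sampling times, and T8 lists all analytes in a single sample.

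**The concern.** Conversion is a question about persons: did any participant produce THC from CBD, and how many? A group average answers a different question. If most values are at or below the assay limit, one or two clear converters are averaged with many near-zero values, and the mean also depends on what is substituted for the non-detects. The T1 pre-dose sample, which could show THC already present before treatment, has no role in the decision. Nor do the metabolites.

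At stake is the safety reading of a primary endpoint. Sections 5.1.1 and 8.1 choose cognitive tests for domains that CBD and/or THC may affect, so whether some participants had THC exposure also bears on how those results are understood.

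**Working it through.** The documents give no rate, threshold or power for conversion (21.4 covers Hypotheses 1a, 1c, 2a, 2b and E), so there is no planned figure to reproduce. The checks below are illustrations.

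**Inputs.** From the documents: 40 randomized 1:1 (section 5.1), so about 20 on CBD; evening dose about 12 h before the morning dose (7.1.5); sampling 45 min after the morning dose (21.3.4). Assumed: concentrations, assay limit, half-lives.

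**1. What the mean and SD show.** If k of 20 reach level c and the rest are 0, then mean = kc/20 and SD = c × √[k(20 − k)/(20 × 19)].

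| k | Mean | SD | SD/mean |
|---|---|---|---|
| 1 | 0.05c | 0.22c | 4.5 |
| 2 | 0.10c | 0.31c | 3.1 |
| 3 | 0.15c | 0.37c | 2.4 |
| 5 | 0.25c | 0.44c | 1.8 |

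With k = 2 and c = 5 ng/ml, the mean is 10/20 = 0.50 and the SD is 5 × √(36/380) = 1.54.

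**2. Whether the SD recovers the count.** It does not. One participant at 7.04 ng/ml and 19 at 0.156 ng/ml give mean (7.04 + 19 × 0.156)/20 = 0.50 and SD (7.04 − 0.156)/√20 = 1.54. The two patterns have the same mean and SD, but one has two high values and the other has one. Median and maximum separate them: 0 and 5 against 0.156 and 7.04.

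**3. Non-detects.** With an assumed assay limit of 1 ng/ml, scoring the 18 non-detects at 0.5 instead of 0 moves the mean from 0.50 to (10 + 18 × 0.5)/20 = 0.95. The plan does not say which applies.

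**4. What a count gives.** 2/20 = 10%, exact 95% CI 1.2% to 31.7%. The chance of seeing at least one converter is 1 − (1 − p)^20, which is 0.64, 0.88, 0.96 and 0.99 for p = 5%, 10%, 15% and 20%. For 0/20 the two-sided 95% upper limit is 1 − 0.025^(1/20) = 16.8%.

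**5. What pre-dose samples would add.** From T2 on, the 45-minute sample is 12.75 h after the evening dose. Under first-order decline it retains 0.5^(0.75/h) of the 12 h residue, where h is the half-life in hours. For assumed half-lives of 1, 2, 4, 8 and 24 h that is 60%, 77%, 88%, 94% and 98%. The pre-dose sample therefore adds only limited information on that residue, and neither sample covers the hours between 45 minutes and 12 hours.

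**6. Which samples have THC and metabolites assigned.**

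| Sample | Protocol Summary, 3.2.3, 5.1.1 | Visit lists, 8.3.2 and 8.3.3 |
|---|---|---|
| T1 pre-dose | Yes (3.2.3) | Yes |
| 45 min, T1 to T7 | Yes | Yes |
| Pre-dose, T3, T4, T6, T7 | CBD and anandamide only | Yes |
| T8 | Not mentioned | Yes |

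The samples in dispute are 4 × 20 = 80 pre-dose samples. T8 adds 20, for a total of 100.

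**The case against.** Several stronger readings are tempting, and the documents do not support them.

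- A reader might infer that conversion is judged from the mean alone. The plan also gives the SD, and an SD three times the mean would suggest a few high values. It would not say how many.
- A reader might infer that the metabolites are ignored. They are primary endpoints, and the Protocol Summary reports each analyte by mean and SD. THC in 21.3.4 may even be shorthand for the panel, since the Endpoint row of the Protocol Summary uses it loosely. What stands is that 21.3.4 does not say so.
- A reader might infer that the decision rests on one early time point and that later conversion is bound to be missed. Section 21.3.4 covers 45-minute samples at T1 to T7, and those from T2 on carry residue of the evening dose.
- A reader might infer that the plan discards pre-dose THC data it will have. Sections 3.2.3 and 5.1.1 do not plan those assays, and nothing settles which text is intended.
- The 16.8% upper limit for 0/20 reflects 20 participants. It is not a flaw in the plan, and no change of statistic removes it.
- No hypothesis in 21.2 concerns conversion, and 21.1 defers a formal SAP until before database lock and unblinding.

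A further objection concerns the remedy: a count above T1 would also pick up undisclosed cannabis use or assay variation, and 8.1 plans THC assays only with CBD, so there is no background rate. This stands, and the fix has to allow for it. The missing placebo comparator is a separate matter.

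**Conclusion.** The point holds in a limited form. The only stated rule for judging conversion is a group summary of THC at 45 minutes, without a participant count, the T1 baseline or an explicit role for the metabolites. It can leave conversion in a minority unseen or unquantified, but does not necessarily do so. With about 20 CBD participants, a single converter's level is diluted 20-fold in the mean, whereas a count would show at least one converter with probability 0.88 if 10% convert. These sizes rest on a full CBD arm of 20; the dilution figure assumes non-converters at zero, and the detection probability assumes that every converter is detectable in a scheduled sample. The documents give no THC concentrations or assay limits to test either assumption. The conflict over pre-dose assays does not depend on any of these assumptions.

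**What to change.** In 21.3.4, and in the formal SAP before unblinding:

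1. Keep the means and SDs. For Delta-9 THC, 11-Hydroxy THC and Carboxy THC, in every sample in which they are assayed, add the number of CBD participants with a quantifiable level above their T1 pre-dose value, with exact 95% CI, and the median and maximum.
2. State how values below the assay limit are handled, including at T1.
3. Report the count with and without participants whose on-study urine drug screen is positive for THC. Section 8.1 places a screen at every in-person visit, although the visit lists omit it at T2 and T5. A positive screen might itself reflect conversion, so both counts are needed and neither settles the cause.
4. Reconcile the Protocol Summary, 3.2.3 and 5.1.1 with the visit lists in 8.3.3 on THC and metabolites in the pre-dose samples at T3, T4, T6 and T7 and at T8.

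Counts are group data, so 21.3.9 need not change. Items 1 to 3 cost wording and slightly more analysis; on the 45-minute and T1 samples they need no new assays. Up to about 100 further THC/metabolite assays (80 pre-dose plus 20 at T8) arise only if the visit lists are kept and those assays were not already planned. They use a different method from CBD and anandamide (8.1), on 1 ml samples stored for no more than 6 months (8.2.1), so the reconciliation should not wait until the end of the trial.
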